### 7.2 Assessment Related to Secondary Endpoints

#### 7.2.1 Cycle Cancellation due to Poor Ovarian Response or Excessive Ovarian Response

The reason for each cycle cancellation will be recorded. Cycle cancellations related to inappropriate ovarian response will include poor and excessive follicular development. Cycle cancellation due to poor follicular development is implemented when the investigator judges that  $\geq 3$  follicles with a diameter  $\geq 17$  mm cannot be reached by stimulation day 20. Cycle cancellation due to excessive follicular development is implemented when  $> 25$  follicles with a diameter  $\geq 12$  mm are observed.

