#### 7.2.4 Proportion of subjects with <4, 4-7, 8-14, 15-19 and $\geq 20$ Oocytes Retrieved

The proportion of subjects with <4 oocytes (low response), 4-7 oocytes (moderate response), 8-14 oocytes (targeted response), 15-19 oocytes (hyperresponse) and  $\geq 20$  oocytes (severe hyperresponse) will be calculated.

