#### Trial-specific Source Data Requirements – Ferring

Source documents need to be preserved for the maximum period of time permitted by local requirements. For each subject enrolled, the investigator will indicate in the source documents that the subject participates in this trial, and will record at least the following information, if applicable:

- Existence of subject (initials, date of birth or age at screening and randomisation, as applicable)
- Confirmation of participation in trial (trial ID, subject ID)
- Informed consent(s) (date and time of obtaining written informed consent(s))
- Eligibility for participation in the trial (documenting all inclusion / exclusion criteria, and successful pituitary down-regulation, if applicable)
- Continuous eligibility for participation in the trial (documenting that none of the withdrawal criteria are met)
- Relevant medical history, infertility history, menstrual history and reproductive history
- Body weight measurements
- Visit dates
- Dates and time of IMP, GnRH antagonist and hCG administration
- Daily dose of IMP administered
- Dates of first day and last day of GnRH agonist and progesterone administration

- Dates and daily doses of concomitant medication
- Date of oocyte retrieval and number of oocytes retrieved
- Date of transfer and number and quality of blastocysts transferred
- Results of  $\beta$ hCG test and ultrasound at clinical and ongoing pregnancy visits
- Pregnancy outcome, i.e. live birth or pregnancy loss, and neonatal health at birth and 4 weeks after birth
- Adverse events (description as well as start/stop date and time)
- OHSS symptoms, preventive intervention (i.e. cycle cancellation), investigations and treatments
- Reason for discontinuation / withdrawal

No specific protocol data can be recorded directly in the e-CRF without prior written or electronic record.

If the trial sites use electronic patient record systems, the sponsor will decide if the electronic patient records qualify for the trial and document the decision. If the electronic patient records system does not qualify for the trial, it may be considered to utilise certified printouts of the data in the electronic patient records system for source data as an exception.

The source data for the endocrine parameters will be available at the central laboratory. Laboratory reports will be available at the sites.

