## 10 Efficacy

### 10.1 General Considerations

The primary objective of the trial is to evaluate the effect of individualised FE 999049 treatment on ovarian response in a long GnRH agonist protocol versus a GnRH antagonist protocol. The primary endpoint is the number of oocytes retrieved.

The estimand of interest is the difference between FE 999049 treatment in the long GnRH agonist protocol versus treatment with FE 999049 in the GnRH antagonist protocol for all randomised subjects, assuming that all subjects start treatment with FE 999049. In the statistical analyses, subjects that discontinue after randomisation but before start of FE 999049 treatment (except for subjects that never started treatment due to the COVID-19 pandemic, which are not included in any analysis) will have their endpoint data imputed from subjects who started FE 999049 treatment in the same protocol, using a multiple imputation method. No imputation will be done for subjects who discontinue the trial after starting FE 999049 treatment. For these subjects, the actual data will be used and not be regarded as missing. Therefore, the number of oocytes retrieved will be regarded as zero and pregnancy outcomes will be regarded as negative.

The trial is descriptive and no formal hypothesis will be tested. The statistical analyses aims at estimating any potential differences between FE 999049 treatment when applied in the two different GnRH protocols. The results will generally be described as an estimated mean treatment difference or treatment ratio and an associated 95% confidence interval.

Since the trial is descriptive without any hypothesis testing, no corrections for multiplicity will be applied.

Analyses and descriptions for ovarian response endpoints and other pharmacodynamics endpoints will be based on the FAS. Analyses and descriptions for pregnancy endpoints will be based on the FAS but excluding subjects that had transfer cancellation due to the COVID-19 pandemic.

Additional descriptions for pregnancy endpoints will be made based on the FAS (i.e. including also the subjects with transfer cancellation due to the COVID-19 pandemic). Analyses and descriptions of safety endpoints and exposure will be based on the safety analysis set.

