Subjects in the FAS that did not start treatment with FE 999049 will not have any data after exposure to FE 999049. For these subjects, post-randomisation data will only be imputed for the purpose of statistical analysis, using multiple imputation techniques. In tables, figures and listings all post-randomisation data from these subjects will be missing. Therefore tables, figures and listings will be based on subjects in the FAS starting treatment with FE 999049, i.e. randomised and exposed subjects (i.e. same as the safety analysis set).

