$$m_{MI} = \frac{1}{1000} \sum_{i=1}^{1000} m_i, \quad SD_{MI} = \sqrt{\frac{1}{1000} \sum_{i=1}^{1000} SD_i^2 + \left(1 + \frac{1}{1000}\right) \left(\frac{1}{1000 - 1}\right) \sum_{i=1}^{1000} (m_i - m_{MI})^2}$$

Where  $m_i$  and  $SD_i$  are the estimated mean differences and standard deviations for the differences for the 1000 copies of the dataset (derived using the delta method), and  $m_{MI}$  and  $SD_{MI}$  are the pooled estimates.

- The mean difference in number of oocytes retrieved between the long GnRH agonist protocol and the GnRH antagonist protocol will be estimated as  $m_{MI}$ , and the 95% CI for the estimate will be calculated as  $m_{MI} \pm 1.96 * SD_{MI}$ .

The assumption underlying the above imputation procedure is that all randomised subjects could have started FE 999049 treatment, and that their outcome would not have differed in any systematic way from the subjects that started FE 999049 treatment.

For subjects who discontinue the trial after start of FE 999049 treatment but before oocyte retrieval the number of oocytes retrieved will be regarded as zero.

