### **10.3 Secondary Efficacy Endpoints**

#### **Proportion of Subjects with Cycle Cancellation due to Poor Ovarian Response or Excessive Ovarian Response**

The proportion of subjects with cycle cancellation due to poor ovarian response or excessive ovarian response will be described. Additional descriptions will be made for the two subgroups based on AMH at screening (<15 pmol/L or  $\geq$ 15 pmol/L) and for the three age strata (<35, 35-37, or 38-40 years).

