## **Proportion of Subjects with <4, 4-7, 8-14, 15-19 and $\geq 20$ Oocytes Retrieved**

The percentage of subjects with <4, 4-7, 8-14, 15-19 and  $\geq 20$  oocytes retrieved will be described in histograms. Additional descriptions will be made for the two subgroups based on AMH at screening ( $<15$  pmol/L or  $\geq 15$  pmol/L) and for the three age strata (<35, 35-37, or 38-40 years).

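### Women cancelled for excessive follicular response are counted in the <4 oocyte class, which the protocol labels low response; show them separately, and split the cancellation endpoint by reason

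*SAP*

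**What the plan says.** **Cancellation.** Protocol 3.5.1, protocol Table 6-2 and SAP 4 cancel a cycle with ≥25 follicles of ≥12 mm. hCG is withheld in both arms, and protocol 6.6.4 sends the woman to end-of-trial assessments, so there is no retrieval.

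**Scoring.** SAP 10.1 says that for women who stop after starting FE 999049 "the actual data will be used and not be regarded as missing". SAP 10.2 gives the result: "before oocyte retrieval the number of oocytes retrieved will be regarded as zero". Neither section distinguishes reasons for stopping.

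**Population of the displays.** SAP 10.1: "Therefore tables, figures and listings will be based on subjects in the FAS starting treatment with FE 999049". Cancelled women are therefore included.

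**Classes.** In SAP 10.3 the percentages in the five classes of "oocytes retrieved will be described in histograms", overall and by AMH and age. There is no row or exclusion for cancelled cycles. The label for the lowest class is in protocol 7.2.4, whose sentence opens "The proportion of subjects with <4 oocytes (low response" and reserves hyperresponse and severe hyperresponse for 15-19 and ≥20 oocytes.

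**Cancellation endpoint.** SAP 10.3: "The proportion of subjects with cycle cancellation due to poor ovarian response or excessive ovarian response will be described". Protocol 7.2.1 groups the two reasons: "Cycle cancellations related to inappropriate ovarian response will include poor and excessive follicular development". It also sets the excessive-response threshold at >25 follicles, not ≥25.

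**The concern.** The two ends of the oocyte distribution carry opposite meanings. Protocol 3.5.4 ties <4 oocytes to the risk of having no blastocyst to transfer, and 15 or more to the risk of early OHSS. A woman whose cycle is cancelled because she responded too strongly is reported at the low end. The protocol's own source-data list (10.1) treats cycle cancellation as an OHSS precaution: "OHSS symptoms, preventive intervention (i.e. cycle cancellation), investigations and treatments".

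This matters most at AMH ≥15 pmol/L. SAP 4.1 says that the treatment difference there will indicate whether the dosing algorithm remains safe and effective in an agonist protocol. A reader of the class display cannot separate too little response from too much, and the cancellation endpoint as worded does not require the two to be shown apart.

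**Working it through.** **1. The plan's own figure.** Protocol 3.5.1 gives a 1.2% incidence of ≥25 follicles among FE 999049-treated women with AMH ≤35 pmol/L in ESTHER-1, and expects 5 cancellations in 400. 0.012 × 400 = 4.8, which rounds to 5; this is 2.4 per arm. The chance of at least one is 1 − 0.988^400 = 99%.

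**2. Rate at AMH ≥15.** Assume that all such women have AMH ≥15. The share of women at AMH ≥15 follows from the ESTHER-1 means in triggered women (10.0 overall, 8.0 and 11.6 by AMH): (10.0 − 8.0)/(11.6 − 8.0) = 0.56, or 112 per arm. Then q = 0.012/0.56 = 2.14% (2.0-2.4% if the share is 60-50%).

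**3. Other zero scores.** At AMH ≥15 the ESTHER-1 mean is 11.6 in triggered women and 11.2 in all randomised (protocol 1.1), implying 1 − 11.2/11.6 = 3.4% zeros. If these include the excessive responders, other stops are o = 3.4 − 2.1 = 1.3%; if not, o = 3.4%.

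**4. Size of the <4 class at AMH ≥15.** Model the counts as negative binomial with mean m and variance m + k·m². The published mean 11.6 and SD 5.9 give k = (5.9² − 11.6)/11.6² = 0.172. That fit gives P(≥15) = 27.4% and P(≥20) = 10.0%, against 28% and 10% in protocol 1.1. It also gives P(≥25) = 3.1%, above the 2.14% of step 2. The two tails must come from one distribution, so for each k from 0.12 to 0.26 the mean is solved to make P(≥25) = 2.14%, and P(<4) is taken from that same distribution.

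Class = P(<4)·(1 − q − o) + q + o, and share = q/class.

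| k | m | P(<4) | class, o = 1.3% | share | class, o = 3.4% | share |
|---|---|---|---|---|---|---|
| 0.12 | 11.8 | 2.9% | 6.3% | 34% | 8.3% | 26% |
| 0.172 | 10.9 | 5.9% | 9.2% | 23% | 11.1% | 19% |
| 0.26 | 9.8 | 11.8% | 14.8% | 14% | 16.7% | 13% |

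In antagonist cycles, excessive-response cancellations are therefore about 13-34% of the <4 class at AMH ≥15.

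**5. Agonist arm.** The documents give no rate. If the mean is assumed 10% higher with the same k and o, cancellation at AMH ≥15 becomes 3.5-3.9% (3.9-4.3 of 112 women) and the share 22-55%. The planned difference in the <4 class (agonist minus antagonist) runs from −1.0 to +0.8 points, so its sign is undetermined. Sampling error is about 1.96·√(2 × 0.08 × 0.92/112) = 7.1 points.

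**6. Overall share.** Protocol 1.1 gives 16% with <4 oocytes at AMH <15, all randomised. With the classes in step 4, the overall <4 share runs from 0.44 × 16% + 0.56 × 6.3% = 10.6% to 0.44 × 16% + 0.56 × 16.7% = 16.4%. The cancelled women are 1.2/10.6 = 11% down to 1.2/16.4 = 7% of it. The middle row with o = 1.3% gives 1.2/12.2 = 10%.

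**7. The threshold.** Protocol 7.2.1 has >25 follicles; protocol 3.5.1, protocol Table 6-2 and SAP 4 have ≥25. A woman with exactly 25 is an excessive-response cancellation under one wording and not under the other.

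**The case against.** The strongest reply is that nothing in the quoted rule is wrong. Zero oocytes is what happened, the estimand takes it as the outcome, and these women indeed have no blastocyst. That stands, and the score should stay. It is also true that the words low response appear only in protocol 7.2.4; the SAP gives numeric classes without labels.

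Much of the information also appears elsewhere: discontinuations by reason (SAP 5), end-of-stimulation follicle counts, including a model for follicles ≥12 mm (SAP 10.3), and OHSS tables (SAP 11.1). The cancellation endpoint does not forbid a split, and SAP 2 puts table format out of scope. A careful reader could recover most of the picture. But none of these outputs is tied to the class display, and none obliges the two cancellation reasons to be reported apart.

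Two stronger readings are tempting. One is that the zeros bias the primary mean difference. Equal cancellation rates produce no net shift, and the documents give no agonist-arm rate from which to derive one. The other is that the labelling reverses the comparison between arms. Step 5 shows that the sign depends on the assumed dispersion, and any effect is far below sampling error. Neither reading is supported.

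**Conclusion.** The point holds as a matter of description. Followed as written, the plan counts the strongest responders in a class that the protocol calls low response, and the cancellation endpoint need not show them apart.

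About 5 women in 400 are expected. This rests on the sponsor's 1.2%, which comes from antagonist cycles. They would be roughly 10% of the <4 class overall (7-11%) and roughly 13-34% at AMH ≥15 in antagonist cycles. The subgroup figures assume that all these women have AMH ≥15, use ≥25 oocytes as a stand-in for ≥25 follicles, and borrow ESTHER-1 means from a trial with no upper AMH limit. Read them as orders of magnitude. The agonist figures rest on a further assumption of 10% more oocytes, with other stops held equal between arms.

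The matter is worth settling because the trial is descriptive by its own account. It does not threaten the primary analysis.

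**What to change.** 1. Keep zero for the primary analysis.
2. In SAP 10.3, oocyte classes: show cycles cancelled for excessive response as a separate row or footnoted count, apart from <4 (low response), by arm, AMH and age. Keep the combined <4 total so that comparison with the all-randomised ESTHER-1 figures in protocol 1.1 remains possible.
3. In SAP 10.3, cycle cancellation: report poor-response and excessive-response cancellations as separate proportions by arm, AMH and age.
4. Reconcile the >25 in protocol 7.2.1 with the ≥25 in protocol 3.5.1, protocol Table 6-2 and SAP 4, because the threshold decides who enters the row. Align the class label in protocol 7.2.4 at the next amendment.

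The cost is a sentence or two in the SAP, one added row and one split row. Protocol 7.2.1 already records the reason for each cancellation, so no new data or model is needed. The drawback is that the new cells will hold about 2-4 women per arm, so counts should accompany the percentages, which will be unstable.

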### **Supplementary analyses and descriptions for the Primary Endpoint**

The primary analysis will be repeated based on subjects in FAS that started treatment with FE 999049, i.e. without using multiple imputations (this is the same as the safety analysis set).

The potential influence of centre differences on the results for the primary endpoint will be investigated by repeating the analyses of the 1000 complete datasets generated above, with the addition of centre and the interaction between centre and age strata as factors in the model.

Additional analyses will be made for two subgroups based on AMH at screening (<15 pmol/L or  $\geq$ 15 pmol/L) and for the three age strata (<35, 35-37, or 38-40 years). These analyses will be based on the 1000 complete datasets used for the primary analyses and will use the same analysis model, except that age stratum will not be included as factor in the age strata analyses and AMH will not be included in the AMH subgroup analyses. The results of the subgroup analyses will be illustrated in a forest plot.

The distribution of number of oocytes retrieved will be described using the empirical distribution and approximated using kernel estimates.

### **10.3 Secondary Efficacy Endpoints**

#### **Proportion of Subjects with Cycle Cancellation due to Poor Ovarian Response or Excessive Ovarian Response**

The proportion of subjects with cycle cancellation due to poor ovarian response or excessive ovarian response will be described. Additional descriptions will be made for the two subgroups based on AMH at screening (<15 pmol/L or  $\geq$ 15 pmol/L) and for the three age strata (<35, 35-37, or 38-40 years).

#### **Proportion of Subjects with Blastocyst Transfer Cancellation after Oocyte Retrieval due to (Risk of) OHSS**

The proportion of subjects with transfer cancellation after oocyte retrieval due to (risk of) OHSS will be described. Additional descriptions will be made for the two subgroups based on AMH at screening (<15 pmol/L or  $\geq$ 15 pmol/L) and for the three age strata (<35, 35-37, or 38-40 years).

## **Number and Size of Follicles on Stimulation Day 6 and End-of-stimulation**

The follicle cohort on stimulation day 6 and end-of-stimulation will be summarised by treatment on the follicle level (number of follicles 8-9 mm, 10-11 mm, 12-14 mm, 15-16 mm and  $\geq 17$  mm) and on the subject level (total number of follicles, size of largest follicle, average follicle size, average size of three largest follicles, and number of follicles  $\geq 8$  mm,  $\geq 10$  mm,  $\geq 12$  mm,  $\geq 15$  mm and  $\geq 17$  mm).

The mean number of follicles  $\geq 8$  mm,  $\geq 10$  mm,  $\geq 12$  mm,  $\geq 15$  mm and  $\geq 17$  mm at end-of-stimulation will (in separate analyses) be compared between the long GnRH agonist protocol and the GnRH antagonist protocol using the same negative binomial regression model as used for the primary endpoint. The analysis will only include subjects in the FAS that started treatment with FE 999049, i.e. multiple imputations will not be used (this is the same as using the safety analysis set).

## **Proportion of Subjects with <4, 4-7, 8-14, 15-19 and $\geq 20$ Oocytes Retrieved**

The percentage of subjects with <4, 4-7, 8-14, 15-19 and  $\geq 20$  oocytes retrieved will be described in histograms. Additional descriptions will be made for the two subgroups based on AMH at screening ( $<15$  pmol/L or  $\geq 15$  pmol/L) and for the three age strata (<35, 35-37, or 38-40 years).

## **Number of Metaphase II Oocytes**

Oocytes undergoing ICSI will have their maturity stage assessed prior to insemination. The total number of metaphase II oocytes will be compared between the long GnRH agonist protocol and the GnRH antagonist protocol using the same analysis method as for the primary endpoint. This analysis will be based on subjects that had all their oocytes inseminated using ICSI. No imputation will be done for subjects having their oocytes inseminated by IVF, or a combination of IVF and ICSI, and consequently no imputation will be done for subjects not starting treatment with FE 999049. Therefore, multiple imputations will not be used and the analysis will be based on subjects in FAS that had all their oocytes inseminated using ICSI (this is the same as subjects in the safety analysis set that had all their oocytes inseminated using ICSI).

## **Fertilisation Rate**

An oocyte is defined as fertilised if it is scored as 2 pronuclei on day 1 after oocyte retrieval. The total number of fertilised oocytes will be compared between the long GnRH agonist protocol and the GnRH antagonist protocol using the same analysis method as for the primary endpoint. The proportion of oocytes becoming fertilised will be summarised by treatment.

## **Number and Quality of Embryos on Day 3 after Oocyte Retrieval**

The number and the quality of embryos on day 3 will be described. The number of embryos and the number of good-quality embryos will be compared between the long GnRH agonist protocol and the GnRH antagonist protocol using the same analysis method as for the primary endpoint. A good-quality embryo is defined as an embryo with  $\geq 6$  blastomeres and  $\leq 25\%$  fragmentation, or with embryo stage classified as compacting/compacted.

## **Number and Quality of Blastocysts on Day 5 after Oocyte Retrieval**

The number and the quality of blastocysts on day 5 will be described, as well as the quality and number of blastocysts transferred.

The number of blastocysts and the number of good-quality blastocysts (grade 3BB or higher) will be compared between treatments using the same analysis method as for the primary endpoint.

## **Circulating Concentrations of FSH, LH, Estradiol, Progesterone and Inhibin B on Stimulation Day 6, End-of-stimulation and at Oocyte Retrieval**

For each parameter, the concentrations on stimulation day 6, end-of-stimulation, and at oocyte retrieval will be described and compared for the long GnRH agonist protocol versus the GnRH antagonist protocol using analysis of variance models with treatment, age stratum, and AMH at screening ( $<15$  pmol/L or  $\geq 15$  pmol/L) as factors. Multiplicative models will be used, i.e. the concentrations will be log-transformed before analysis. The results of the analyses will be back-transformed and presented as estimated geometric means for each parameter, and the mean ratios for long GnRH agonist protocol versus GnRH antagonist protocol with 95% confidence intervals.

The analyses will be based on subjects in the FAS starting treatment with FE 999049, i.e. multiple imputations will not be used (this is the same as using the safety analysis set). Values below the lower limit of quantification (LLOQ) will be estimated with LLOQ/2.

## **Total Gonadotropin Dose and Number of Stimulation Days**

The total gonadotropin dose and the number of stimulation days will be described for each of the two protocols and for subgroups based on age strata and AMH at screening.

Number of stimulation days, total dose, and the average daily dose will be compared between long GnRH agonist protocol and the GnRH antagonist protocol using an analysis of variance model with treatment, age stratum, and AMH at screening ( $<15$  pmol/L or  $\geq 15$  pmol/L) as factors. This analysis will be based on subjects in the FAS that started treatment with FE 999049, i.e. multiple imputations will not be used (this is the same as using the safety analysis set).

